10.3. Informed Consent

All study subjects must sign an EC approved ICF according to 2011:ISO14155 guidelines, GCP guidelines and all applicable national regulations. Potential subjects must be informed as to the purpose of the study and the potential risks and benefits known or that can be reasonably predicted or expected as described in the written consent form. The subject shall have sufficient opportunity to consider participation in the study; a subject cannot be led to believe that they are waiving their rights as a subject or the liability of the Sponsor or Investigator. Subjects are then invited to sign and date the consent form, indicating their consent for enrollment. The Investigator will retain the original copy of the signed consent form in the study files. A duplicate copy shall be provided to the subject.

10.4. Risk – Benefit Analysis

A. Study Related Risks

Possible risks that may occur as a result of study procedures are:

- This study involves the use of x-ray and fluoroscopic evaluation. X-ray exposure is cumulative over a lifetime and total exposure should be kept to a minimum. However, if the x-ray exposure when participating in the study is equivalent to the exposure the subject would receive if they chose not to participate in the study, there is no additional risk associated with this study.
- As a result of participating in the study there could be a risk of loss of protected subject information confidentiality. All applicable confidentiality standards and data protection and privacy laws will be followed by the Sponsor to ensure that data collected is handled in confidence. Data will be coded and handled only by appropriately qualified and authorized personnel.

Risks related to the general surgical procedures and exposure to x-ray for preoperative planning are not considered here because these risks are equivalent whether the subject participates in the study or not.

B. Study Related Benefits

Because the surgery and all the follow-up visits are the same as when the subject would not participate in this study, there are no additional medical benefits associated by participating in this study. The information gained from this study may help to improve the existing instruments used for the implantation of the SL-PLUS® MIA Ti/HA femoral hip stem and in consequence improve the treatment of patients that need to undergo THA.

11. MONITORING PROCEDURES

11.1. Source Documentation

Investigators are responsible for obtaining and maintaining complete subject health information in the medical record for each subject (source documents). Examples of source documents are: hospital records, clinic and office charts, memoranda, dispensing records, subject questionnaires, clinic evaluation transcriptions, operative notes, x-rays, radiology reports, blood collection reports and shipment records, and research subject files. CRFs may be used as source documents if they represent data collected for the study and are the location that data is initially recorded.

As a minimum entry in the medical records, the PI shall ensure that clinical records are clearly marked to indicate that the subject is enrolled in a particular clinical study and if they completed per protocol or discontinued early and the reason.

11.2. Direct Access

This study may be monitored by the Sponsor or a qualified person designated by the Sponsor. This qualified person could be an employee of the Sponsor or of a contract research organization (Sponsor's agent).

The Investigator will provide Sponsor, Sponsor's agents, EC and regulatory agencies with direct access to all source data/documents to permit study-related monitoring, audits, EC review, and regulatory inspections.

11.3. Site Qualification Visit (SQV)

A SQV may be performed by the Sponsor prior to the execution of a clinical agreement to ensure that all Investigators have the appropriate training, staff, facilities and resources to adequately conduct the study.

11.4. Prior to Study Initiation

The Investigator must ensure the activities below are completed prior to the initiation of the study and provide supporting documentation to the Sponsor:

- **Clinical Study Agreement:** must be fully executed with the site and the Sponsor and any other appropriate party.
- **Documentation of Qualifications:** a current, signed and dated Curriculum Vitae (CV) for Investigator and for all key members of Investigator study site team listed on the Delegation of Authority Log must be submitted to the Sponsor prior to the study and updated as applicable to staff changes and confirmed at close out visit.
- **Conflict of Interest:** all participating Investigators are required by ISO 14155 to provide details of conflict of interest (including financial, if applicable) according to local regulations. This information must be updated promptly by the Investigator and submitted to the Sponsor if any changes occur through the duration of the study and for one year following completion of the study.

11.5. Site Initiation Visit (SIV)

A SIV to provide training on the specifics of the study, site obligations and expectations of study conduct will be performed by the Sponsor following execution of the Clinical Study Agreement and documented EC approval.

11.6. Interim Monitoring Visits (IMVs)

Due to the short length of the study no IMVs will be performed.

11.7. Sponsor Audits and Regulatory Inspection

Quality assurance auditors, whether an employee of the Sponsor or its designee, may evaluate study conduct at the study sites. These parties must have access to any and all study reports and source documentation, regardless of location and format.

11.8. Close Out Visit (COV)

A study COV will be performed by the Sponsor or designee to retrieve and account for all remaining clinical data and to resolve outstanding queries. During study close-out, the monitor will review the Investigator Master File to ensure required documents and records are on file, confirm the disposition of any other ancillary items used for the study, and review regulatory requirements regarding records retention and EC reporting requirements.

During the COV the monitor will further:

- verify the informed consent process
- perform source data verification
- verify that source documentation is complete and available
- ensure compliance with the protocol

11.9. Documentation of Site Visits

Activities associated with a monitoring visit (SQV, SIV, COV) will be documented by the monitor. This includes:

- monitor visit log on site
- a Follow-Up letter to the Investigator following each visit summarizing the visit and detailing any site deficiencies and action items to clarify or address issues noted

11.10. Data Handling and Record Keeping Requirements

CRFs will be supplied by the Sponsor. Subjects will be identified by a study number and subject identification code. Only the Investigator site will have the key to identify individual subjects.

The Investigator is responsible for the timely and accurate completion of CRFs. All documents related to the study must be securely archived at the study site or in a central archive.

Data required according to this protocol are to be recorded on the CRFs at the time of the scheduled visits. Once a subject is enrolled, completed CRFs should be sent to the Sponsor, either by fax or by e-mail, as soon as possible, and no later than 10 working days upon completion of the CRFs.

11.11. Data Recording and Record Retention

Clinical research records shall be stored in a manner that ensures privacy, confidentiality, security and accessibility of the records both during and after the conduct of the study. The Investigator/Institution will take measures to prevent accidental or premature destruction of those documents. The Investigator must retain essential study documents for at least 2 years after the date the study is terminated or completed. If the Investigator needs to dispose of the documents, the Sponsor should be contacted for approval prior to disposal or destruction. For discontinued product, the essential documents will be retained until at least 2 years have elapsed since the formal discontinuation (via notification of the FDA or other regulatory agency) of clinical development of the investigational product. The Investigator will retain these documents for a longer period if required by the applicable local laws.

If the responsible Investigator retires, relocates, or withdraws from responsibility of keeping the study records, custody must be transferred to a person who will accept the responsibility. The Sponsor must be notified in writing of the name and address of the new custodian. Under no circumstance shall the Investigator relocate or dispose of any study documents before having obtained written approval from the Sponsor.

12. DEVIATIONS FROM PROTOCOL

A protocol deviation is an instance of failure, intentionally or unintentionally, to follow the requirements of the protocol. Protocol deviations include but are not limited to: deviations from inclusion/exclusion criteria, endpoint variable criteria, study visits outside the window, and GCP guidelines.

12.1. Protocol Deviation Reporting Requirements

Deviations must be reported to the Sponsor through the specially designed Protocol Deviation Log as soon as reasonably possible.

When protocol deviations affect the scientific soundness of the study, or the rights, safety or welfare of the study subjects, the Investigator must also report protocol deviations to the EC of the study site. It is the responsibility of the PI to inform the EC of the incident, per local requirements. The local EC should be consulted on protocol deviation reporting requirements.

Investigators and all study staff (staff at site and at Sponsor) are responsible for ensuring adherence to study protocol. During the monitoring visits, the Sponsor representative will review all deviations with the Investigator. If a deviation is discovered outside of a monitoring visit, it should be evaluated via phone, email or letter. Appropriate measures to address the occurrence, additional monitoring visits, or audit of the study should be taken, which may include defining and implementing a Corrective and Preventive Action (CAPA).

13. PUBLICATION POLICY

13.1. Multicenter Publication

The Sponsor may invite the Investigator to participate in a multicenter publication of the study results, in which case it will be ensured that the documents submitted for publication comply with the publisher's requirements for authors and contributors. If the publisher has no such requirements, it will be ensured that the publication meets the authorship and contributorship requirements as stated in the current Smith & Nephew Global Policy and Procedure relating Scientific Disclosures. Also, the Sponsor will select a publisher based on mutual agreement with the Investigators, who are invited to participate in the publication.

13.2. Investigator Publication

The Investigator may publish his/her own data subject to the following restrictions:

- the multicenter manuscript must be published prior to Investigators publishing their own data;
- the manuscript shall be submitted to the Sponsor for review prior to submitting the manuscript for publication;
- the manuscript must reference the study multicenter manuscript.

## 2. REVISION HISTORY

Version Number	Reason for Change or Change Control Number	Document Author
0.1	Initial Draft Version	[name]
0.2	Draft Version	[name]
0.3	Draft Version	[name]
0.4	Draft Version	[name]
0.5	Draft Version	[name]
0.6	Draft Version	[name]
0.7	Draft Version	[name]
0.8	Draft Version	[name]
0.9	Draft Version	[name]
1.0	Final Version	[name]

## 3. ACRONYMS

Table 1: Acronyms

Acronyms	Term
ADE	Adverse Device Effects
AE	Adverse Event
CI	Confidence Interval
CRF	Case Report Form
DD	Device Deficiency
FAS	Full Analysis Set
$m_{50}$	Median
Max	Maximum
Min	Minimum
MRT	Multiple Response Table
N	Available Records (count)
SADE	Serious Adverse Device Effects
SAE	Serious Adverse Event
SAP	Statistical Analysis Plan
SD	Standard Deviation
THA	Total Hip Arthroplasty

## 4. INTRODUCTION

With an increasing life expectancy, the demand of total hip arthroplasties is rising while the success of the hip implant depends to the position of the femoral stem. The correct position of a cemented hip stem is planned preoperatively. During surgery, the final

Confidential & Proprietary

position of the rasp should correspond to the preoperatively determined position and the same position should be adopted by the cemented femoral stem.

The SL-PLUS™ MIA Ti/HA femoral hip stem study is going to evaluate the difference between the final position of the stem and the last trial rasp.

## 5. STUDY OBJECTIVES

The study objective is to evaluate if there is a difference between the femoral position of the last trial rasp and the final implant position of the SL-PLUS™ MIA Ti/HA femoral hip stem.

### **Primary Endpoint:**

The primary endpoint is the mean difference D between the position of the last trial rasp and the final implant position of the SL-PLUS™ MIA Ti/HA femoral hip stem. The difference D is determined by analyzing standardized fluoroscopic images taken during surgery.

The difference D is given in mm and is defined as  $D = x_1 - x_2$  with  $x_1$  being the distance between the shoulder of the trial rasp and the tip of the greater trochanter and  $x_2$  being the distance between the shoulder of the implant and the tip of the greater trochanter.

The study hypothesis is defined as:

$H_0$ : The null hypothesis is that there is no mean difference between the position of the last trial rasp and the final implant position of the SL-PLUS™ MIA Ti/AH femoral hip stem.

$H_1$ : The alternative hypothesis is that there is a mean difference between the position of the last trial rasp and the final implant position of the SL-PLUS™ MIA Ti/AH femoral hip stem.

### **Secondary Endpoints:**

The secondary endpoints include a measurement of leg length discrepancy preoperatively and after insertion of the SL-PLUS™ MIA Ti/HA femoral hip stem. In addition, intraoperative complications will be collected.

## 6. INVESTIGATION PLAN

### 6.1. STUDY DESIGN

This is an observational, single arm, prospective, multi-center, case series study to collect intraoperative data from 40 subjects implanted with the SL-PLUS™ MIA Ti/HA femoral hip stem at 4 sites in Europe.

Data from eligible subjects, who have provided written and informed consent for the collection of their coded data, will be recorded on specially designed case report forms (CRFs).

Confidential & Proprietary

No follow-up visits after surgery is planned for study participants. Therefore, total study duration for study participants is completed with surgery.

A final data analysis describing the study outcome is planned after completion of study assessments.

## 6.2. RANDOMIZATION PLAN

No randomization algorithm was followed for patient recruitment.

## 6.3. SAMPLE SIZE DETERMINATION

The following hypotheses will be tested:

$H_0$ : The null hypothesis is that there is no mean difference between the position of the last trial rasp and the final implant position of the SL-PLUS™ MIA Ti/AH femoral hip stem.

$H_1$ : The alternative hypothesis is that there is a mean difference between the position of the last trial rasp and the final implant position of the SL-PLUS™ MIA Ti/AH femoral hip stem.

$$H_0: \mu = 0 \text{ vs. } H_1: \mu \neq 0$$

In 2007, a non-published cadaver test was performed to measure the difference  $D$  between the position of the last trial rasp and the implant position of the SL-PLUS™ MIA Ti/AH femoral hip stem. A total of 4 femoral hip stems were implanted into the cadaveric femur. The range of the measured difference was found to be between 0mm and 6mm. However, it is most likely that the maximum difference will be greater 6mm when more cases are studied. To compensate for the small number of evaluated cases, the anticipated variation in  $D$  will be extended to 10mm with an estimated standard deviation of 2.5mm. A correlation  $\rho$  between the distances  $x_1$  and  $x_2$  is certainly positive but it is unknown how strong the correlation is. The standard deviation  $sd$  of the difference  $D$  has the following relationship with the standard deviations  $sd_1$  and  $sd_2$  for distances  $x_1$  and  $x_2$ :

$$sd^2 = sd_1^2 + sd_2^2 - 2 \rho sd_1 sd_2$$

Since  $\rho > 0$  and assuming that  $\rho = 0$  will lead to a larger  $sd$  and therefore a larger sample size. If assumed that  $sd_1 = sd_2$ , then  $sd^2 = 2sd_1^2$ . So assuming  $sd_1$  and  $sd_2$  being equal, the  $sd$  will also lead to a larger sample size. Therefore, assuming that the correlation is zero and allowing for both standard deviations  $sd_1$  and  $sd_2$  to be 2.5mm is a conservative approach for computing sample size.

According to orthopaedic surgeons, the maximum difference between the position of the rasp and implant without clinical significance is considered to be 2mm. The standard deviations of  $sd_1$  and  $sd_2$  are estimated as approximately 2.5mm estimated based on the assumptions above and data for the range of difference.

The sample size calculation is based on a two-sided test. The significance level and power of the study are chosen to be 0.05 and 0.90; the minimum mean difference  $\Delta$  is identified as 2 mm; the standard deviations  $sd_1$  and  $sd_2$  are 2.5mm; the correlation between  $x_1$  and  $x_2$  is set to 0. The following formula can be used to calculate the sample size:

Confidential & Proprietary

$$N \geq \frac{2(T_{N-1,\alpha/2} + T_{N-1,\beta})^2 sd^2}{\Delta^2}$$

The SAS POWER procedure is used to compute the sample size and at least 35 subjects are needed for the study.

#### 6.4. VISIT SCHEDULE AND VISIT WINDOW

Table 1 shows the evaluations completed at each visit.

**Table 2: Visit Schedule**

Study Visit Schedule	Pre-Operative	Surgery Peri-Operative
Patient Information and Informed Consent	x	
Inclusion/Exclusion Criteria	x	
Demographics/Medical History	x	
Radiographic assessment	x	
Operative Data Collection		x
Fluoroscopic assessment		x
Measurement of leg length discrepancy	x	x
Adverse Event Assessment	x*	x
End of Study/Exit		x

\* if applicable

#### 6.5. PRIMARY ENDPOINT EVALUATION

Confidential & Proprietary

Once a subject has completed the informed consent procedure and signed the Informed Consent Form (ICF), the Principal Investigator (PI) or delegated study research staff can complete the screening process with the subject. All potential subjects who undergo the screening process will be documented on a Screening and Enrollment Log, on which reasons for exclusion from or denial to participate should be noted. The primary endpoint analysis of the mean difference D between the position of the last trial rasp and the final implant position of the SL-PLUS™ MIA Ti/HA femoral hip stem will be based on full analysis set (FAS) population. The FAS population includes all subjects implanted with a SL-PLUS™ MIA Ti/HA femoral hip stem device in combination with a Smith & Nephew cup with consecutive enrollments to the study. Subjects being a screen failure (CRF plate 99, question 1. Screen Failure Yes) will be excluded from the FAS. A primary endpoint analysis of a sub-group might be performed excluding subjects with low image quality as per defined image review criterias (e.g. trochanter not visible). This depends on the assessment of the independent Image Reviewer.

## 6.6. SECONDARY ENDPOINTS EVALUATIONS

The secondary endpoint analysis of measurement of leg length discrepancy preoperatively and after insertion of the SL-PLUS™ MIA Ti/HA femoral hip stem (and in addition, collecting intraoperative complications) will also be based on full analysis set (FAS) population.

## 6.7. SAFETY

Safety evaluations include the listing of Adverse Events (AE), Serious Adverse Events (SAE), Adverse Device Effects (ADE) and Serious Adverse Device Effects (SADE).

Additionally, listings about Device Deficiency (DD) will be reported.

## 7. STATISTICAL METHODS

### 7.1. GENERAL REPORTING CONVENTIONS

Analyses will be generated using Stata version 15.0 or higher.

General summary statistics for **numeric data** include the available records (N), the mean (Mean), the standard deviation (SD), the median ( $m_{50}$ ), the minimum (Min), and the maximum (Max) value. Summary statistics can also be grouped by all relevant categorical variables, for example between lateral / standard or Pre-Op / Surgery/Peri-Op.

For **categorical data**, the count / available records (N) and percent (%) of data will be presented with the percent based on the number of subjects within the data. Additionally, bar charts will be provided.

---

 To eliminate the potential for selection bias, Investigators should consecutively pre-screen all subjects undergoing THA with the SL-PLUS™ MIA Ti/HA femoral hip stem. In order to do so, only the existing information obtained per standard routine medical procedures will be used. No study-specific screening procedures, activities or questionnaires will be performed during pre-screening.

For **missing data**, a complete accountability report, along with the explanation for lost-to-follow-up, death, revision and withdrawn subjects, is to be provided in the study report. No other adjustment or imputations will be made for missing data.

**Multiple response** answers (marked with “check all that apply”) offer several ways to determine the number of valid observations. By default, all cases with at least one valid response are taken into account. All other observations are treated as missing. Furthermore, one might want to consider cases with complete information only and neglect all cases with one or more missing values (Stata option “casewise”). The results will be provided as multiple response table (MRT).

For any **two-group comparison**, a paired or unpaired t-Test (depending on the data) will be performed. All t-Tests will be fitted using Stata “ttest” command. No 2+ group comparison is planned in this study, so no baseline must be chosen.

If not mentioned otherwise, all results are reported as a two-sided significance test. Significance values of less than 5% ( $p < 0.05$ ) are considered as statistically significant. Any confidence intervals (CI) will be based on 95% CIs.

## 7.2. STUDY POPULATIONS

All subjects who meet the study inclusion and exclusion criteria will be included in the statistical analysis. **Subjects being a screen failure as documented on “End of Study” – CRF (plate 99) (answer “yes”) will be excluded from the statistical analysis.** Statistical analyses will be conducted for demographics, pre-operative information, surgical information and safety data. Demographics will include, but not limited to, gender, age, weight and height. Pre-operative information and surgical information will include any data collected as defined in this protocol. Safety data will include adverse events, serious adverse event, adverse device effect, serious adverse device effect, unanticipated serious adverse device effect, and device deficiency.

Descriptive statistics for continuous variables will include mean, median, minimum, maximum, standard deviation, and 95% confidence interval, if appropriate. Descriptive statistics for discrete variables will include count and percentage.

Subgroup analyses will be provided if they are necessary. The following sections define the details of primary endpoint and secondary endpoints analyses.

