5.3. Subject Exclusion Criteria

Subject:

- requires the use of a ceramic-on-ceramic bearing
- has infections, acute or chronic, local or systemic
- has severe muscle, nerve or vascular diseases that endanger the respective limb
- has lack of bone substance or defective bone quality that jeopardizes the stable seating of the prosthesis
- has any concomitant disease that may jeopardize implant function
- has a known allergy to study device or one or more of its components
- requires a revision surgery and has extensive bone defects
- has diagnosis of an immunosuppressive disorder
- is pregnant

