7.2. Enrollment

Subject enrollment occurs at the time of surgery. Every subject that receives the study device will be considered enrolled in the study. If a subject has provided consent and completed screening, and for any reason does not receive study device, the subject will not be considered enrolled in the study.

Therefore pre-operative CRFs will not be submitted to the Sponsor until the subject is actually enrolled (treated with study device) in the study.

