7.3. Conditions for Study Termination

Reasons for termination of study participation are described below.

A. Screening Failure

Subjects who have provided informed consent but did not receive the study device are considered screen failures. The reason for screening failure must be captured on the Screening and Enrollment Log maintained in the Investigator Master File. No CRFs will be collected.

B. Voluntary Withdrawal

Study participation is voluntary and subjects may withdraw at any point during the study without giving their reason for doing so. CRFs are collected until time point of withdrawal.

C. Subject Termination by Investigator

The Investigator should withdraw subjects from the study in case the study device cannot be implanted during surgery for any reason.

Subjects that do not receive the study device are not considered as enrolled and will be documented on the Screening and Enrollment Log.

D. Study Termination

The Sponsor may choose to discontinue the study at any time. In which case, the subjects will be followed up according to the standard practice of the site.

E. Study Site Discontinuation

A specific study site in this multicenter study may also warrant termination under the following conditions:

- non-compliance to Good Clinical Practice (GCP) or protocol
- failure to enroll subjects

- inaccurate or incomplete data
- unsafe or unethical practices
- safety or performance considerations

In this case, enrolled subjects will be followed up according to the standard practice of the site.

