**Table 24: Implanted Components: Acetabular Liner**

Acetabular Liner Type	Total N = xx (%)
R3™ XLPE Acetabular Liners	

Confidential & Proprietary

SL-PLUS™ MIA Ti/HA femoral hip stem  
 Statistical Analysis Plan  
 Final Version 1.0  
 2017 09 21

R3™ INTL Delta Ceramic Liners	
Other	
Acetabular Liner Size	Total N = xx (%)
28	
32	
36	

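### Safety tables have no population of their own: SAP 7.2 and protocol 9.2 tie them to eligibility, while enrolment and the FAS are tied to implantation

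*SAP*

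**What the plan says.** The sentence "All subjects who meet the study inclusion and exclusion criteria will be included in the statistical analysis" stands in SAP 7.2, the section on study populations, and word for word in protocol 9.2. Each section then sets its scope: "Statistical analyses will be conducted for demographics, pre-operative information, surgical information and safety data". Each lists AEs, SAEs, ADEs, SADEs, unanticipated SADEs and device deficiencies as safety data.

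SAP 7.2 adds one express exclusion. Subjects marked as screen failures on the End of Study CRF ("answer “yes”) will be excluded from the statistical analysis") are left out. Protocol 7.3 defines that status by implantation: "Subjects who have provided informed consent but did not receive the study device are considered screen failures".

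Enrolment is also defined by implantation. Protocol 7.2 states: "Every subject that receives the study device will be considered enrolled in the study".

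SAP 6.5 bases the primary analysis on the FAS: subjects implanted with the stem together with a Smith & Nephew cup, consecutively enrolled, less screen failures. Under SAP 6.6 the secondary endpoints, intraoperative complications among them, "will also be based on full analysis set (FAS) population". SAP 6.7 and 8.5.1 describe the safety outputs, including the number and percent of subjects with an AE, without naming a population.

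**The concern.** A patient can receive the stem and later be found to have breached an eligibility criterion. That patient is enrolled and is not a screen failure as the protocol defines it, yet does not belong to the group that SAP 7.2 says will be analysed. No safety set overrides that sentence, so it is the only population rule that reaches the AE, SAE, ADE, SADE and device deficiency tables.

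Two things are at stake. First, an adverse event in an implanted patient could be left out of the safety tables on grounds unrelated to exposure, when exposure is the usual basis for a safety denominator. Some exclusion criteria plausibly bear on operative risk, for example "has lack of bone substance or defective bone quality that jeopardizes the stable seating of the prosthesis", so the omission may not be neutral. Second, protocol 6.1.2 records intraoperative complications through the safety reporting process of section 8. The complication endpoint and the AE tables therefore draw on the same records under different population rules, and one event could be reported against two denominators.

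**Working it through.** **Comparing the population rules.** All rows below are implanted subjects. The columns apply protocol 7.2, SAP 6.5/6.6 and the natural reading of SAP 7.2.

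| Implanted subject | Enrolled | Complication endpoint (FAS) | Safety tables |
|---|---|---|---|
| Eligible, in FAS | yes | yes | yes |
| Ineligible, in FAS | yes | yes | no |
| Eligible, outside FAS (other cup or not consecutive) | yes | no | yes |
| Ineligible, outside FAS | yes | no | no |

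The rules agree only in the first row. In the second and third rows the same event counts in one output and not in the other. In the fourth it counts in neither. The FAS therefore could not simply be adopted as the safety set.

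Nothing settles which rule prevails. Protocol 9.2 does not mention an FAS, and SAP 9 says the protocol's planned analyses are unchanged.

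**Inputs for the illustration.** The planned number of subjects is 40. Protocol 9.3 obtains it from 35 evaluable subjects and a 12% allowance for missing data: 35 / (1 − 0.12) = 39.8, rounded up to 40. That figure reproduces and is not in dispute. The documents give no number of implanted but ineligible subjects and no expected event rate. I assume k = 1 to 3 such subjects among 40 implanted, all in the FAS, with one SAE in the whole study, occurring in one of the k.

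**All implanted subjects.** The rate is 1/40 = 2.5%. Exact (Clopper-Pearson) 95% limits:
- Lower: 1 − 0.975^(1/40) = 0.0006, i.e. 0.1%.
- Upper: the p that solves (1 − p)^40 + 40p(1 − p)^39 = 0.025, which is p = 0.132, i.e. 13.2%.

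**Eligible subjects only.** The rate is 0/(40 − k) = 0%. The exact two-sided 95% upper limit is 1 − 0.025^(1/(40 − k)):
- k = 1: 0/39, upper limit 9.0%.
- k = 2: 0/38, upper limit 9.3%.
- k = 3: 0/37, upper limit 9.5%.

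Under these assumptions the SAE table shows none. If the event is also an intraoperative complication, the complication summary shows 1/40 for it.

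**When the ineligible patient has no event.** With k = 1 and one SAE in an eligible patient, the filtered rate is 1/39 = 2.6% against 1/40 = 2.5%. The filter then raises the rate slightly. Understatement is thus conditional on who has the event.

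**The case against.** The strongest reply is that the exclusion is inferred. The sentence says that eligible subjects will be included; it does not say that only they will be. The one express exclusion is screen failure, and when the SAP wants subjects out it says so: Table 47 marks screen failures as excluded, while Table 5 has a row for unmet eligibility criteria, with the reason, and no such note. The FAS is the only named analysis set and SAP 8.1 also uses it for disposition, so FAS throughout is a possible reading. This stands in part: removal is the natural reading, not a stated instruction. But if the sentence is not read as a population definition, the safety outputs have no defined population, and the same repair is needed.

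A second reply is that the event is not lost. Protocol section 8 collects AEs from implantation onward with no eligibility condition, SAEs reach the sponsor within 24 hours, and a complication in an FAS patient is still reported under SAP 6.6. That is correct. The defect lies in the reported tables and rates, not in collection or expedited reporting.

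A reader might also infer that the plan expects ineligible patients to be implanted. The documents do not go that far. Protocol 12 and SAP Table 5 show only that eligibility breaches are possible. The row "R3™ INTL Delta Ceramic Liners" in SAP Table 24 might suggest ceramic-on-ceramic pairings, an exclusion criterion, but Tables 22 and 24 list heads and liners separately and may be generic pick lists. Bone quality is assessed before surgery (protocol 6.1.1), and nothing says that an operative finding makes a subject ineligible in retrospect.

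**Conclusion.** The point holds as an inconsistency in a stated rule. SAP 7.2 and protocol 9.2 link the safety analysis to eligibility, protocol 7.2 and the FAS link their populations to implantation, and no safety set resolves the difference. On the natural reading, implanted but ineligible patients are left out of the safety tables.

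Two stronger readings are tempting and are not supported. One is that every analysis is restricted to eligible subjects. That fits protocol 9.2 taken alone but not the SAP, because 6.5 and 6.6 assign the primary and secondary endpoints to the FAS. The other is that the safety rates will be biased downward. They will be understated only if an excluded patient has an event.

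The contrast of 0/39 with 1/40 rests on two assumptions: one ineligible patient, and the only SAE falling in that patient. It shows that with 40 subjects a single omission can turn an observed serious event into none. It is not a forecast. No hypothesis test is affected, since safety is reported descriptively. The change should be made, but the point does not threaten the primary analysis.

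**What to change.** - In protocol 9.2 and SAP 7.2 and 8.5.1, state that all safety tables (SAP 12.6 to 12.8) and the intraoperative complication summary include every subject who received the study stem, regardless of eligibility deviations, cup used or consecutive enrolment.
- Reconcile SAP 7.2 with the FAS in 6.5 and 6.6. Moving the complication summary to all implanted subjects requires a matching edit in 6.6; otherwise a new contradiction replaces the old one.
- List implanted but ineligible subjects with the criterion each one failed.
- Use any eligibility filter only in a sensitivity analysis.

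The cost is a few sentences in the two documents, with mutual agreement on the protocol amendment and possibly ethics committee approval under protocol 10.2. No new data are needed, because AEs are already recorded from implantation. The downside is that the reported event rate may be slightly less favourable.
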